The orexin antagonist lemborexant is FDA approved for treatment of insomnia. Lemborexant acts on both OX1R and OX2R and has shown efficacy in sleep initiation and maintenance compared to placebo on polysomnography and patient-report.(Rosenberg et al., 2019) It has demonstrated long-term safety and effectiveness without physical dependence or rebound insomnia.(Murphy et al., 2017; Yardley et al., 2021) Compared to suvorexant, another orexin antagonist, lemborexant has greater selectivity and stronger binding for orexin receptors. Suvorexant has secondary effects on the adenosine receptor and dopamine transporter whereas lemborexant only has weak binding to melatonin 1. These differences may increase risk of misuse for suvorexant more than lemborexant.(Asakura et al., 2021) In addition, Lemborexant's longer half-life (17-19h) may be advantageous for reduction of cravings during the day.(Landry et al., 2021)

In people with AUD, insomnia is a common problem that is associated with alcohol craving and relapse.(He et al., 2019) Standard treatment for AUD with naltrexone improves cravings and other AUD outcomes, but does not improve sleep. In some cases, naltrexone may have a detrimental effect on sleep.(Anton et al., 2006; Panin & Peana, 2019) Lemborexant may be able to target both alcohol craving/urges and insomnia when added to standard treatment with naltrexone.

Aims and hypothesis

Our primary goal is to evaluate the effects of naltrexone plus lemborexant augmentation compared to naltrexone plus placebo on cue-induced and non-cued alcohol craving scores. Our secondary goals are to evaluate the effects of this combination on sleep quality using actigraph data.

Hypotheses: H1: we hypothesize that the group receiving naltrexone plus lemborexant augmentation will have a greater decrease in cue-induced and non-cued alcohol craving scores than naltrexone plus placebo. H2: we hypothesize that the group receiving naltrexone combined with lemborexant will experience a greater improvement on objective sleep measures.

Significance of the problem

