Alcohol use disorder (AUD) and insomnia are highly comorbid in our psychiatric inpatients. In people with AUD, insomnia may be persistent and is associated with alcohol craving and relapse. Standard treatment for AUD with naltrexone improves cravings and other AUD outcomes, but does not improve sleep. In some cases, naltrexone may have a detrimental effect on sleep. Insomnia is associated with higher severity of depression, anxiety, and suicidality. Adequate treatment of both alcohol cravings and insomnia may improve overall outcomes.

Design and methods

The study will be a randomized, double-blind, placebo-controlled clinical trial of naltrexone plus placebo versus naltrexone plus lemborexant conducted at The Menninger Clinic on inpatients with alcohol use disorder. Recruitment will occur on patients admitted to a Menninger inpatient unit over a 12-month period. Because the average length of stay at The Menninger Clinic is 2 to 4 weeks, the study period will last 2 to 4 weeks depending on the patient's length of stay. We plan to enroll 10 patients and randomize half to lemborexant plus naltrexone and half to placebo plus naltrexone using a computer-generated randomization scheme.

All participants will receive a standard treatment program with pharmacotherapy for their psychiatric conditions, CBT, DBT, individual therapy, and group therapy during their inpatient admission. Subjects will be randomly assigned to either naltrexone plus placebo or naltrexone plus lemborexant. For all patients, naltrexone will be given at 50 mg/day. For the lemborexant augmentation group, lemborexant will be given at 10mg at bedtime. Dose reductions due to tolerability will be permitted at the discretion of the investigator. Blinding will be ensured by use of a matching placebo for lemborexant 10mg using over-encapsulation. Participants and study personnel will be blinded to the study drug. Medications will be administered by nursing staff. All participants will be exposed to alcohol-related cues using virtual reality technology at baseline, at the end of week 2 or end of week 4.

Safety: Safety assessments will be collected weekly throughout the study. These assessments will consist of monitoring and recording of adverse events and periodic measurement of vital signs.

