Assessment and Outcomes Measures (Tables 1 and 2): As part of the Menninger Clinic inpatient evaluation, each patient will be given a medical examination, including physical exam and laboratory testing on admission. Assessments will include baseline EKG, CBC, BMP, liver profile, pregnancy test (females), and urine drug screen. This information is part of the health record and will be collected for screening and analysis.

Clinical diagnoses including alcohol use disorder will be assessed using the structured clinical interview for DSM-5 (SCID-5). Alcohol use disorder severity will be measured using the alcohol dependence scale (ADS). We will also be using an actigraph to measure total sleep time and wake after sleep onset. Cue-induced alcohol cravings will be assessed using the Alcohol Urge Questionnaire (AUQ) and non-cued alcohol craving will be assessed using the Penn Alcohol Craving Scale (PACS).

Table 1: Initial Assessment, Sleep, Mood, and Suicide risk

Measure	Instrument	Screening	Daily	Weekly	Discharge
DSM-5 Diagnoses (including Alcohol use disorder)	Structured Interview for DSM-5 (SCID-5)	X			
Alcohol Use Disorder Severity	Alcohol Dependence Scale (ADS)	X			
Total Sleep Time, wake after sleep onset	ActiGraph wGT3X-BT	X		X	X

Table 2: Alcohol Craving Measures

Measure	Instrument	Baseline	Week 1	Week 2	Week 3	Week 4
Cue-induced alcohol craving	Alcohol Urge Questionnaire (AUQ)	X	x	x	x	x
Non-cued alcohol Craving	Penn Alcohol Craving Scale (PACS)	X	X	X	X	X

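### Craving has no discharge reading, so a patient who leaves before the planned follow-up cue session has no post-baseline AUQ taken after cue exposure

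*Combined protocol and SAP*

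**What the plan says.** Craving is the primary outcome. Aims and hypothesis states: "Our primary goal is to evaluate the effects of naltrexone plus lemborexant augmentation compared to naltrexone plus placebo on cue-induced and non-cued alcohol craving scores". Actigraph sleep measures are secondary.

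Assessment and Outcomes Measures has two schedules. The one headed "Table 1: Initial Assessment, Sleep, Mood, and Suicide risk" marks actigraphy at screening, weekly and at discharge. The one headed "Table 2: Alcohol Craving Measures" marks AUQ and PACS at baseline and at each of weeks 1 to 4. It has no discharge column, and its AUQ row is labelled as cue-induced craving at every one of those times.

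Design and methods sets follow-up by length of stay: "Because the average length of stay at The Menninger Clinic is 2 to 4 weeks, the study period will last 2 to 4 weeks". On the cue sessions it says: "All participants will be exposed to alcohol-related cues using virtual reality technology at baseline, at the end of week 2 or end of week 4".

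Statistical Analysis plans a hierarchical linear model (HLM) for repeated measurements within patients, with adjustment for variables that differ significantly between dropouts and the rest. No minimum stay is stated, and no rule says what is measured when discharge falls between scheduled readings.

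**The concern.** The secondary outcome has a closing measurement tied to the day the patient leaves. The primary outcome does not. Its follow-up sits on fixed weeks, while the length of follow-up depends on the stay, and 2 to 4 weeks is described as an average, so shorter stays are possible.

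The gap is sharpest for cue-induced craving, because an AUQ score reflects a response to cues only if cues were presented. Between baseline and the end of week 2 no exposure is planned. If leaving early is related to craving, response or tolerability, the cue-exposed readings that go missing would not be a random subset. That matters in a pilot whose stated purpose is to obtain unbiased effect sizes from 10 patients.

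**Working it through.** The plan gives no power or precision figure, so there is none to reproduce. The check counts scheduled readings by discharge day and then sizes the effect of losing cue-exposed readings.

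**Step 1: readings available by discharge day.** Inputs are the weekly columns of Table 2 and the cue-session sentence in Design and methods. Week k is assumed to be read on day 7k. The wording on cue sessions can mean week 2 for some patients and week 4 for others, or whichever week the stay reaches, so both cases are shown.

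| Discharge day | Post-baseline AUQ and PACS (Table 2) | Cue sessions if week 2 applies | Cue sessions if week 4 only |
|---|---|---|---|
| before 7 | 0 | 0 | 0 |
| 7–13 | 1 | 0 | 0 |
| 14–20 | 2 | 1 | 0 |
| 21–27 | 3 | 1 | 0 |
| 28 | 4 | 1 (2 if both are held) | 1 |

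Only the first row gives no follow-up craving data of any kind. The second row gives one AUQ and one PACS but no cue exposure.

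**Step 2: the two passages side by side.** Table 2 calls the AUQ cue-induced every week. Design and methods provides cues at baseline and at week 2 or week 4 only. On that schedule the AUQs at weeks 1 and 3 are uncued despite the row label. If cues were instead meant to be shown weekly, a patient leaving on days 7–13 would have one cued reading, and the gap would shrink to departures before week 1 plus the days after the last weekly reading. The documents do not settle which is intended.

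**Step 3: chance of losing at least one patient.** The documents give no distribution of stays, so the proportion q leaving before day 14 is assumed. With 10 patients the chance is 1 − (1 − q)^10:

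- q = 5%: 0.40 (0.5 patients expected)
- q = 10%: 0.65 (1 expected)
- q = 20%: 0.89 (2 expected)
- q = 30%: 0.97 (3 expected)

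**Step 4: precision of a cue-exposed comparison at one time.** The half-width of the 95% interval for the arm difference, in SD units, is t(0.975; n1 + n2 − 2) × √(1/n1 + 1/n2):

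- 5 v 5: 2.306 × 0.632 = 1.46
- 5 v 4: 2.365 × 0.671 = 1.59 (1.586/1.458, +9%)
- 4 v 4: 2.447 × 0.707 = 1.73 (1.730/1.458, +19%)
- 4 v 3: 2.571 × 0.764 = 1.96 (1.963/1.458, +35%)

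Losses are split as evenly as possible between arms; an uneven split is wider. These widths apply to a contrast of the cue-exposed AUQ alone. They do not apply to PACS or to the HLM on weekly readings.

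**The case against.** A reader might infer that the primary outcome is lost for everyone who leaves early. The documents do not support that. The primary goal covers both cued and non-cued craving, Table 2 schedules both instruments at week 1, and the HLM keeps partial series. A patient discharged on day 11 contributes a PACS and an AUQ. One discharged on day 18 contributes two of each, plus a cue session if week 2 applies. For the same reason, the half-widths above cannot be read as the precision loss of the planned analysis.

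A reader might also infer that early departures will be common. The plan gives no stay distribution and says the study period itself runs 2 to 4 weeks, so zero losses is possible. That leaving relates to craving is plausible but not documented.

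The plan does address attrition, by adjusting for variables that differ between dropouts and the rest. With 10 patients few differences would reach significance, and adjustment cannot supply an outcome that was never measured.

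Finally, the missing column is not by itself the cause of the lost cue session. A discharge AUQ without cues would not be a cued reading, and placing it in the cue-induced row would add to the confusion. This objection stands, and it shapes the fix. What remains is that the schedule as written provides no cue-exposed follow-up for departures before the planned session, and no closing craving reading for anyone discharged between weekly visits.

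**Conclusion.** The point holds in a limited form. As written, a patient discharged before the end of week 2 has no post-baseline AUQ taken after cue exposure, and a patient assigned to week 4 who leaves sooner may have none. Those who reach week 1 still contribute to the HLM; only those who leave before that reading give no follow-up craving data.

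One to three losses would widen a single-time cued comparison by 9% to 35%, and no losses would leave it unchanged. This rests on an assumed number of early departures, weekly readings on day 7k, and Design and methods being the correct account of when cues are shown. Bias could be added if departure relates to craving; its size cannot be derived from the documents. The change is worth making because it is cheap and the trial is small.

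**What to change.** 1. Add a discharge column to Table 2 with PACS and AUQ.
2. If a patient is to be discharged before the planned follow-up cue session, hold that session, with its AUQ, on the last feasible day before discharge, where the investigator judges it appropriate. It replaces the missed session, so no patient has more cue sessions than planned.
3. Reconcile Table 2 with Design and methods: mark each AUQ reading as cued or uncued, and state whether week 2, week 4 or both apply to a given patient.
4. Use only cued AUQ readings for cue-induced craving, and enter every reading in the HLM at its actual study day.

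The cost is one table column and a few sentences in the protocol and analysis section. The downsides are some cued readings after shorter treatment, scheduling at short notice, and a cue exposure close to discharge. Abrupt departures may still be missed, so the number of patients without a cued follow-up reading should be reported by arm.

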Statistical Analysis: Descriptive statistics and bivariate tests will be used to inspect distributional properties of sample demographics and clinical outcomes at baseline, within the sample and between participant subgroups (e.g., gender, age, AUD severity). All outcome measures and safety assessments will be summarized weekly over the study period. Additionally, variables that significantly differ between participants who dropped out of the study and those who did not will be controlled statistically in our hypothesis testing to minimize any systematic bias due to attrition. Hierarchical linear modeling (HLM) will be conducted to examine the effects of receiving naltrexone plus lemborexant augmentation versus naltrexone plus placebo, while properly accounting for (a) the dependency of observations—i.e., correlation of repeated measurements (level 1) within participants (level 2) and (b) any difference due to receiving the treatments in a different group. Appropriate covariance structures will be determined in a preliminary analysis (i.e., intercept-only model) based on model fit (e.g., adjusted Akaike Information Criterion, Bayesian Information Criterion). Statistical significance will be determined at 0.05 alpha level.

Sample Size and Power: The study is a pilot trial with a purpose of obtaining *unbiased* effect sizes for naltrexone plus lemborexant augmentation prescribed to a small number of adult patients with AUD. No formal power calculation is

applicable because this is a first-in-human study and relevant data is not available in the literature.

References

Alcohol Facts and Statistics / National Institute on Alcohol Abuse and Alcoholism

(NIAAA). (n.d.). Retrieved October 14, 2021, from

<https://www.niaaa.nih.gov/publications/brochures-and-factsheets/alcohol-facts-and-statistics>

Anton, R. F., O'Malley, S. S., Ciraulo, D. A., Cisler, R. A., Couper, D., Donovan, D.

M., Gastfriend, D. R., Hosking, J. D., Johnson, B. A., LoCastro, J. S.,

Longabaugh, R., Mason, B. J., Mattson, M. E., Miller, W. R., Pettinati, H. M.,

Randall, C. L., Swift, R., Weiss, R. D., Williams, L. D., ... COMBINE Study

Research Group, for the. (2006). Combined Pharmacotherapies and

Behavioral Interventions for Alcohol DependenceThe COMBINE Study: A

Randomized Controlled Trial. *JAMA*, 295(17), 2003–2017.

<https://doi.org/10.1001/jama.295.17.2003>

Asakura, S., Shiotani, M., Gauvin, D. V., Fujiwara, A., Ueno, T., Bower, N.,

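### Choosing covariates by a significance test of dropouts against completers is a poor guard against attrition bias in 10 patients, and as worded it does not exclude post-randomisation variables

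*Combined protocol and SAP*

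**What the plan says.** In the combined protocol and SAP, the Statistical Analysis section states that "variables that significantly differ between participants who dropped out of the study and those who did not will be controlled statistically", and gives the place and purpose as "in our hypothesis testing to minimize any systematic bias due to attrition". The wording is mandatory and reaches the tests of both H1 (craving) and H2 (sleep). The only significance level given is general: "Statistical significance will be determined at 0.05 alpha level". Sidedness is not stated, and the dropout screen has no level of its own.

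The same paragraph opens with bivariate comparisons at baseline, with gender, age and AUD severity as examples of subgroups. The sentence directly before the rule is about on-study data: "All outcome measures and safety assessments will be summarized weekly over the study period". The rule itself gives no list of candidates, no restriction to baseline, no cap on the number of covariates and no named test. The main analysis is a hierarchical linear model (HLM) of repeated measurements. No missing-data assumption or sensitivity analysis is stated.

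On size and follow-up, Design and methods says "We plan to enroll 10 patients and randomize half to lemborexant plus naltrexone and half to placebo plus naltrexone" and "the study period will last 2 to 4 weeks depending on the patient's length of stay". No dropout rate is anticipated, and nothing separates a week-2 discharge from a dropout. The Sample Size and Power section says "The study is a pilot trial with a purpose of obtaining *unbiased* effect sizes" and offers no power calculation.

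**The concern.** This screen is the only protection against attrition bias that the plan describes. A significance test in so few patients reflects the number of dropouts more than the size of any imbalance. A real imbalance will usually go unflagged, and some of what is flagged will be chance. The screen also looks only at the link with dropout and not at the link with the outcome, although a variable needs both to produce bias.

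The second issue is which variables may enter. If the screen is run on everything collected, it can select on-treatment sleep, craving or adverse events. These may be consequences of lemborexant. The protocol's own rationale is that insomnia goes with craving and that lemborexant may act on both, so on-treatment sleep is a plausible step on the path to the craving outcome. Adjusting for it would answer a different question from the one in H1 and would work against the stated aim of unbiased effect sizes.

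**Working it through.** **Inputs.** From the documents: 10 patients, 5 per arm (Design and methods); alpha 0.05 (Statistical Analysis). Assumed, because the documents are silent: two-sided tests, 1 to 5 dropouts, and the number and type of candidate variables. The split 5 + 5 = 10 is the only figure of the plan that can be reproduced. There is no effect size, SD, power or dropout rate from which to rebuild it.

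**1. Can the screen find a real difference?** With m dropouts and 10 − m completers, a two-sample t-test has 8 df (critical value 2.306) and noncentrality d × √(m(10 − m)/10). The smallest attainable p is 2/C(10, m) for the rank-sum test. For Fisher's test it is 1/C(10, m) when m is 1 to 4, and 2/C(10, 5) when m = 5, where two tables are equally extreme.

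| Dropouts | Noncentrality at d = 1 | t-test power at 1 SD | Difference for 80% power | Smallest Fisher p | Smallest rank-sum p |
|---|---|---|---|---|---|
| 1 | √0.9 = 0.949 | 13% | 3.4 SD | 0.10 | 0.20 |
| 2 | √1.6 = 1.265 | 20% | 2.5 SD | 0.022 | 0.044 |
| 3 | √2.1 = 1.449 | 25% | 2.2 SD | 0.008 | 0.017 |
| 4 | √2.4 = 1.549 | 28% | 2.1 SD | 0.005 | 0.010 |
| 5 | √2.5 = 1.581 | 29% | 2.0 SD | 0.008 | 0.008 |

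At 0.5 SD the t-test power is 7% to 11%. For a binary feature carried by 80% of dropouts and 20% of completers, Fisher power is 0%, 11%, 30%, 38% and 38% for 1 to 5 dropouts. With two dropouts, for example, both must carry the feature and none of the 8 completers: 0.8² × 0.8⁸ = 0.107.

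**2. How often does chance add a covariate?** For k independent continuous null variables, P(at least one flag) = 1 − 0.95^k:
- k = 5: 23%
- k = 10: 40%
- k = 15: 54%

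Binary variables under Fisher's test are flagged far less often. At prevalences of 0.2 to 0.5, the rate per variable is 0% with 1 dropout, 0.2% to 0.7% with 2, and 0.5% to 1.6% with 3. Ten independent binary candidates with 3 dropouts therefore give at most 1 − 0.984¹⁰ = 15%. Correlated candidates also lower the figure.

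**3. What does a chance covariate cost if it is a baseline variable?** The check was a simulation of 5 + 5 patients with one outcome per patient, 3 dropouts unrelated to outcome, 10 null baseline variables and the t-test rule (20,000 runs). Type I error was 4.9% and the mean estimate 0.004 against a true value of 0, so there is no bias. The mean 95% CI width rose from 2.82 to 2.97 SD, a ratio of 2.97/2.82 = 1.05. In a separate run, forcing in 1, 2 or 3 noise covariates widened the interval from 2.84 to 3.11, 3.45 and 3.96 SD. These figures are for a participant-level contrast by ordinary least squares, not for the planned HLM.

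**4. What if a post-randomisation variable enters?** As an illustration, with values chosen for the purpose, let treatment shift a mediator by 0.8 SD, the mediator slope be 0.6 and the direct effect 0.4. The total effect is 0.4 + 0.6 × 0.8 = 0.88. The simulated estimate without adjustment was 0.87; with adjustment for the mediator it was 0.40. Adjustment removes the indirect part, 0.48 of 0.88, or 55%.

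**The case against.** The strongest defence is that the rule is meant for baseline variables. The paragraph opens with baseline comparisons, and baseline is where dropouts have complete data. On that reading selection depends on dropout status and not on the treatment estimate, and step 3 shows no bias and a small loss of precision. That stands. A reader might infer that the plan intends to adjust for on-treatment variables, or that the rule biases the effect in any case. The documents support neither: the text permits post-randomisation covariates by not excluding them, but it does not plan them.

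Three other tempting readings go too far.
- **The screen cannot detect attrition bias at all.** This is literally true only for one dropout under an exact or rank test. Otherwise power is low, not zero.
- **Most of what it flags is chance.** This depends on the mix. With 3 dropouts and 10 continuous candidates, one true 1-SD difference gives 0.25 expected true flags against 9 × 0.05 = 0.45 false. Two give 0.50 against 0.40.
- **Every added covariate costs one of 8 degrees of freedom.** This holds for a participant-level contrast. H1 concerns a greater decrease, so treatment-by-time is a natural contrast in the HLM. In a random-intercept check with 10 patients and 5 visits, a participant-level main-effect covariate left that contrast unchanged in balanced data. With two early dropouts the largest change was 0.037, against a mean SE of 0.152.

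It is also fair that adjusting for true baseline predictors of dropout is a legitimate aim, since missing at random may depend on them. The fault lies in choosing them by significance, without a list, in 10 patients.

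**Conclusion.** The point holds in a limited form. As a safeguard the rule is weak: about 13% to 29% power at 1 SD across 1 to 5 dropouts. It can also admit noise, in about 40% of trials with 10 independent continuous null candidates and fewer if they are binary or correlated. For baseline variables the price is some precision in participant-level contrasts, not bias. Bias from the rule arises only if post-randomisation variables are used, which the wording leaves open; the 55% in step 4 illustrates the mechanism and does not predict this trial.

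These sizes rest on assumed dropout counts, two-sided tests, assumed candidate sets and the least-squares simplification. The point should be fixed because a better alternative costs almost nothing. It is not critical: this is a 10-patient pilot, its size limits inference far more than this rule does, and with no dropouts the rule has no effect.

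**What to change.** In Statistical Analysis, replace the rule with text that:

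- fixes the covariates in advance: the baseline value of the outcome, and optionally one named baseline predictor of dropout, such as the ADS score;
- states that no post-randomisation variable is used as a covariate;
- fits the planned HLM by likelihood to all randomised patients with every available visit, and names missing at random as the assumption;
- describes dropouts by arm without significance tests, after defining dropout as distinct from planned discharge within the 2-to-4-week period.

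A sensitivity analysis that shifts the missing values in the lemborexant arm (delta adjustment) is optional at 5 patients per arm.

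The cost is SAP wording only; no design or data-collection change is needed. One pre-specified participant-level covariate takes a participant-level contrast from 8 to 7 df (critical value 2.306 to 2.365). The downside is that baseline predictors of dropout that are not named in advance are no longer adjusted for.

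### The Statistical Analysis section gives baseline craving and sleep values no stated role in the HLM; on its most natural reading, the arm contrast is an unadjusted change from baseline with 5 patients per arm

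*Combined protocol and SAP*

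**What the plan says.** Under Aims and hypothesis, H1 is that the lemborexant arm "will have a greater decrease in cue-induced and non-cued alcohol craving scores than naltrexone plus placebo". Table 2 schedules AUQ and PACS at baseline and at weeks 1 to 4. Table 1 schedules actigraphy at screening, weekly and at discharge.

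Design and methods gives the size and allocation: "We plan to enroll 10 patients and randomize half to lemborexant plus naltrexone and half to placebo plus naltrexone". The allocation is made "using a computer-generated randomization scheme", and no stratification or balancing on baseline craving is mentioned.

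The Statistical Analysis section then says that "Hierarchical linear modeling (HLM) will be conducted to examine the effects of receiving naltrexone plus lemborexant augmentation versus naltrexone plus placebo", with repeated measurements at level 1 and participants at level 2. It does not name the dependent variable (weekly score or change), the time term, an arm-by-time term or the role of the baseline score. Baseline outcomes are to be inspected with descriptive and bivariate methods. The one explicit covariate rule admits variables that differ significantly between dropouts and completers. The model is also meant to account for "any difference due to receiving the treatments in a different group", which is too vague to count as baseline adjustment.

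**The concern.** A hypothesis about a decrease, tested in a repeated-measures model that has baseline as its first row, leads most analysts to an arm-by-time contrast with each arm's baseline mean estimated freely. That contrast subtracts the observed baseline difference in full. In a randomised trial any such difference is due to chance, and only part of it is expected to persist to follow-up. The arm that happens to start higher therefore tends to fall further even if the drug does nothing.

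With 5 patients per arm the chance difference is often large. Under Sample Size and Power, the purpose of this pilot is to obtain effect sizes, so the single realised estimate is its main product. Leaving the model open also means that the choice between an adjusted and an unadjusted contrast can be made after the baseline imbalance has been seen.

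**Working it through.** The plan gives no power, effect size or SD, so there is no figure of its own to reproduce. What follows is an impact calculation in units of the outcome SD.

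**Inputs**
- From Design and methods: 10 patients, half to each arm, so n = 5 per arm; no balancing on baseline craving stated.
- From Table 2: a baseline value and up to four weekly values.
- Assumed: baseline-to-follow-up correlation ρ of 0.3, 0.5 or 0.7, with 0.8 added to show where the result turns; equal variances; no dropout.

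**Step 1: what the contrast is.** With baseline as an outcome row, free arm means and complete data, the arm-by-visit contrast at a visit is the difference between arms in (visit mean − baseline mean). This is the change-score contrast. A linear time term shares the dependence on baseline, because baseline enters the slope with a negative weight.

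**Step 2: size of the chance baseline difference d.**
- SD of d = √(2/n) = √(2/5) = 0.632.
- P(|d| > 0.5) = 2 × (1 − Φ(0.5/0.632)) = 0.43; by the same formula P(|d| > 0.8) = 0.21.
- Mean |d| = 0.632 × √(2/π) = 0.505.

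**Step 3: effect on the estimate.** With no drug effect and a baseline difference d, the expected follow-up difference is ρd, so the expected change contrast is ρd − d = −(1 − ρ)d. For the typical gap of 0.505 this is 0.7 × 0.505 = 0.35, 0.5 × 0.505 = 0.25 and 0.3 × 0.505 = 0.15 SD at ρ = 0.3, 0.5 and 0.7.

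**Step 4: precision, one post-baseline visit.**
- Change-score variance: 2(1 − ρ)(2/n).
- Baseline-adjusted variance: (1 − ρ²)(2/n)(1 + 1/(2n − 4)), where 1 + 1/(2n − 4) = 7/6.
- Ratio, adjusted to change: (1 + ρ)/2 × 7/6.

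| ρ (assumed) | Shift at typical gap (SD) | SE, change | SE, adjusted | Variance ratio |
|---|---|---|---|---|
| 0.3 | 0.35 | 0.748 | 0.652 | 0.76 |
| 0.5 | 0.25 | 0.632 | 0.592 | 0.875 |
| 0.7 | 0.15 | 0.490 | 0.488 | 0.99 |
| 0.8 | 0.10 | 0.400 | 0.410 | 1.05 |

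The ratio equals 1 when (1 + ρ)/2 = 6/7, that is ρ = 5/7, or about 0.71.

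**Step 5: simulation check** (40,000 trials per setting, exchangeable correlation, no drug effect).
- Over all randomisations, both the unadjusted and the adjusted estimates averaged 0.00.
- In trials with d above 0.5 SD in one direction (probability 0.43/2, about 0.21; mean gap about 0.86 SD), the unadjusted estimate averaged −0.60, −0.43 and −0.25 SD at ρ = 0.3, 0.5 and 0.7. The adjusted estimate averaged about 0.00.
- With the mean of four post-baseline visits as outcome and ρ = 0.5, the SD of the estimate fell from 0.501 unadjusted to 0.417 adjusted. The one-visit figures therefore understate the gain when visits are pooled.

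**The case against.** The strongest objection is that the model is unspecified. A reader might infer that the HLM is known to analyse change without baseline adjustment. The section does not say so: the decrease comes from the hypothesis, and a baseline covariate or a common baseline mean would both be compatible with the text. This stands. The unadjusted contrast is only the most natural reading, and what the documents establish is that no role for baseline is stated.

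A reader might also infer that regression to the mean biases the effect size and so defeats the stated aim of unbiased estimates. It does not. Regression to the mean is equal in expectation in two randomised arms, and the unadjusted contrast averages to the truth over randomisations. The error is conditional on the imbalance drawn, with added variance on top.

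A third inference would be that the effect is diluted to 2/3 (2-week stay) or 4/5 (4-week stay) because the baseline visit is averaged in. That requires a pooled arm main effect, equal visit weights and a constant effect from week 1. The documents state none of these, and H1 points away from a pooled main effect.

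Finally, the gain at this size is modest. In a further simulation with one post-baseline visit, and allowing for the lost degree of freedom, the mean 95% confidence interval was about 5% narrower at ρ = 0.5, about 1% wider at 0.7 and about 4% wider at 0.8. This stands as a limit on the precision argument. It leaves untouched the argument that the realised estimate should not move with a chance baseline gap.

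**Conclusion.** The point holds as an omission with a clear and inexpensive remedy. It is not a demonstrated error in a stated model. Baseline craving and sleep values are collected but have no stated place in the HLM. Baseline craving would become a covariate only if it happened to differ significantly between dropouts and completers among 10 patients.

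If the arm-by-time reading is followed, a typical chance gap moves the realised effect size by 0.15 to 0.35 SD over assumed correlations of 0.7 down to 0.3. That is large enough to mislead whoever uses the estimate. The chance-imbalance figures in Step 2 follow from the documents' sample size, given equal variances and an approximately normal difference in means. The shift and variance figures also depend on the assumed correlation, and the variance figures on a single post-baseline visit.

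**What to change.** For AUQ, PACS and each actigraphy measure (total sleep time, wake after sleep onset), state the dependent variable and fixed effects of the HLM, and prespecify one of the following:

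- post-baseline values as outcome, with arm, week, arm-by-week and the baseline value of that same measure as covariate; or
- a constrained longitudinal model with baseline kept as an outcome row, one common baseline mean for both arms, and arm-by-week terms after baseline only.

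Apply the chosen form whatever imbalance is observed and whatever the dropout comparison shows. For actigraphy, say which record is the baseline; Table 1 labels the first one as screening.

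Two further choices are separate and are not part of this change. One is which visit carries the main contrast: Design and methods schedules cue exposure at baseline and at the end of week 2 or week 4, while Table 2 lists AUQ weekly, and the two need to be reconciled first. The other is whether the attrition covariate rule is kept.

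The cost is SAP wording and no new data. It uses at most 1 degree of freedom and loses a little precision if the correlation exceeds about 0.71 (SE 0.410 against 0.400 at 0.8, one post-baseline visit).
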